6. DOSE MODIFICATIONS

Dose escalation guidelines

No doses escalation will be permitted on this study.

Dose modifications

For patients who do not tolerate the protocol-specified dosing schedule, dose adjustments are permitted in order to allow the patients to continue the abemaciclib treatment. Any changes in drug administration will be recorded in the clinical trial record.

For patients who do not tolerate the protocol-specified dosing schedule, adjustments are recommended in order to allow the patient to continue the study treatment. Refer to Section 7.3.1 for dose level reductions. For purposes of EDC entry, dose modification is defined as dose reductions and dose holds.

General guidelines for dose modifications

- For grade 1 and tolerable grade 2 treatment-related toxicities, with the exception of pneumonitis, patients may continue at the current dose of abemaciclib.
- For intolerable grade 2 treatment-related toxicities, with the exception of pneumonitis, dosing should be interrupted until resolution to grade 1 or lower followed by dose reduction to the next dose level.
- For grade 3 or grade 4 treatment-related toxicity, that is not considered by the investigator to be life-threatening, dosing should be interrupted and the patients should be followed until the toxicity resolution to grade 1 or lower. Following recovery from grade 3 or grade 4 events, study treatment may continue following a dose reduction to the next dose level, if, in the opinion of the Investigator, the patient continues to experience clinical benefit. For any grade 3 or grade 4 treatment-related toxicity that is considered by the investigator to be life-threatening, permanently discontinue study treatment.

All dose modifications, interruptions or discontinuations must be based on the worst preceding toxicity as graded by the NCI Clinical Toxicity Criteria version 5

Patients whose treatment is interrupted or permanently discontinued due to an AE must be followed until resolution or stabilization of the event. Patients requiring interruptions greater than 2 cycle (56 days) should be discontinued from abemaciclib treatment. All patients will be followed for safety until 30 days after the last dose of abemaciclib.

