7.3.4 General Guidance for Hepatic Monitoring

Alanine aminotransferase (ALT) and aspartate aminotransferase (AST) elevation are considered as ADR with the use of abemaciclib. **The following information in Table 7-3 is to be followed for hepatic monitoring:**

Table 7-3: Dose Modification and Management — Increased ALT/AST

Monitor ALT/AST prior to the start of abemaciclib therapy, every 2 weeks for the first 2 months, monthly for the next 2 months, and as clinically indicated.	
CTCAE Grade	Abemaciclib Dose Modifications
Grade 1 ($>\text{ULN}-3.0 \times \text{ULN}$) Grade 2 ($>3.0-5.0 \times \text{ULN}$)	No dose modification is required.
Persistent or Recurrent Grade 2, or Grade 3 ($>5.0-20.0 \times \text{ULN}$) that does not resolve with maximal supportive measures within 7 days to baseline or Grade 1	Suspend dose until toxicity resolves to baseline or Grade 1. Resume at next lower dose.
$\geq\text{Grade 2} (>3.0 \times \text{ULN})$ with total bilirubin $>2 \times \text{ULN}$, in the absence of cholestasis	Discontinue abemaciclib.
Grade 4 ($>20.0 \times \text{ULN}$)	Discontinue abemaciclib.

To ensure patient safety the investigator should collect specific recommended clinical information and follow-up laboratory tests as shown below in Table 7-4.

Details for hepatic monitoring depend upon the severity and persistence of observed laboratory test abnormalities. If a study patient experiences elevated ALT/AST 5×ULN and elevated TBL 2×ULN, or ALT/AST 8×ULN, liver tests, including ALT, AST, TBL, direct bilirubin, gamma-glutamyl transferase (GGT), and creatine phosphokinase (CPK), should be repeated within 3 to 5 days to confirm the abnormality and to determine if it is increasing or decreasing. If the abnormality persists or worsens, clinical and laboratory monitoring should be initiated by the investigator, based on the hepatic monitoring tests below.

Table 7-4: Hepatic Monitoring Tests for a Hepatic Treatment Emergent Abnormality.

Hematology	Clinical Chemistry
Hemoglobin	Total bilirubin
Hematocrit	Direct bilirubin
Erythrocytes (RBCs - red blood cells)	Alkaline phosphatase (ALP)
Leukocytes (WBCs - white blood cells)	Alanine aminotransferase (ALT)
Differential:	Aspartate aminotransferase (AST)
Neutrophils, segmented	Gamma-glutamyl transferase (GGT)
Lymphocytes	Creatine kinase (CK)
Monocytes	
Basophils	
Eosinophils	
Platelets	
Cell morphology (RBC and WBC)	
Coagulation	Other Chemistry
Prothrombin time, INR (PT-INR)	Acetaminophen

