Serology	Acetaminophen protein adducts
Hepatitis A virus (HAV) testing:	Alkaline phosphatase isoenzymes
HAV total antibody	Ceruloplasmin
	Copper
	Ethyl alcohol (EtOH)
	Haptoglobin
	Immunoglobulin IgA (quantitative)
	Immunoglobulin IgG (quantitative)
	Immunoglobulin IgM (quantitative)

HAV IgM antibody	Phosphatidylethanol (PEth)
Hepatitis B virus (HBV) testing:	Urine Chemistry
Hepatitis B surface antigen (HBsAg)	Drug screen
Hepatitis B surface antibody (anti-HBs)	Ethyl glucuronide (EtG)
Hepatitis B core total antibody (anti-HBc)	Other Serology
Hepatitis B core IgM antibody	Anti-nuclear antibody (ANA)
Hepatitis B core IgG antibody	Anti-smooth muscle antibody (ASMA) ^a
HBV DNA ^c	Anti-actin antibody ^b
Hepatitis C virus (HCV) testing:	Epstein-Barr virus (EBV) testing:
HCV antibody	EBV antibody
HCV RNA ^c	EBV DNA ^c
Hepatitis D virus (HDV) testing:	Cytomegalovirus (CMV) testing:
HDV antibody	CMV antibody
Hepatitis E virus (HEV) testing:	CMV DNA ^c
HEV IgG antibody	Herpes simplex virus (HSV) testing:
HEV IgM antibody	HSV (Type 1 and 2) antibody
HEV RNA ^c	HSV (Type 1 and 2) DNA ^c
Microbiology	Liver kidney microsomal type 1 (LKM-1) antibody
Culture:	
Blood	
Urine	

^a Not required if anti-actin antibody is tested.

^b Not required if anti-smooth muscle antibody (ASMA) is tested.

^c Reflex/confirmation dependent on regulatory requirements, testing availability, or both.

General Guidance for Venous Thromboembolic Events

VTE has been identified as an ADR for abemaciclib in combination with endocrine therapy. However, in studies with single-agent abemaciclib use in the metastatic breast cancer or other tumor types, including NSCLC, no increased rates of VTEs were observed as compared to the incidence of VTEs for these particular patient populations who were treated with other

anticancer agents. At this time, the mechanism underlying the association between abemaciclib and the occurrence of VTEs is not known. Venous thromboembolic events have been reported with other CDK4 and 6 inhibitors, and ET is known to be associated with the occurrence of VTEs. Monitor patients for signs and symptoms of deep vein thrombosis and pulmonary embolism and treat as medically appropriate.

Table 7: Dose Modification and Management — Venous Thromboembolic Events

CTCAE Grade	Abemaciclib Dose Modifications
Grade 1 or 2	No dose modification is required.
Grade 3 or 4	Suspend dose and treat as clinically indicated. Abemaciclib may be resumed when the patient is clinically stable.

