7.3.5 General Guidance for Hematology Toxicity and Dose Modification

Hematologic toxicities including neutropenia, leukopenia, anemia, and thrombocytopenia have been observed in patients treated with abemaciclib, and causality has been established. Severe (Grade 3 and 4) neutropenia was observed in patients receiving abemaciclib. Patients should be monitored closely for signs of infection, anemia, and bleeding. **The following instructions from Table 7-5 must be used to manage hematologic toxicities.**

Table 7-5: Dose Modification and Management — Hematologic Toxicities

Monitor complete blood counts prior to the start of abemaciclib therapy, every 2 weeks for the first 2 months, monthly for the next 2 months, and as clinically indicated.	
CTCAE Grade	Abemaciclib Dose Modifications
Grade 1 or 2	No dose modification is required.
Grade 3	Suspend dose until toxicity resolves to \leq Grade 2. Dose reduction is not required.
Grade 3, recurrent, or Grade 4	Suspend dose until toxicity resolves to \leq Grade 2. Resume at next lower dose.
Patient requires administration of a blood cell growth factor	Suspend abemaciclib dose for at least 48 hours after the last dose of blood cell growth factor and until toxicity resolves to \leq Grade 2. Resume abemaciclib at next lower dose unless the dose was already reduced for the toxicity that led to the use of the growth factor.

7.3.6 General Guidance for Nonhematologic Toxicities (excluding diarrhea, increased ALT and ILD/Pneumonitis) Monitoring

Nonhematologic toxicities excluding diarrhea

- Grade 1 or 2: No dose modification is required.
- Persistent or recurrent Grade 2 toxicity that does not resolve with maximal supportive measures within 7 days to baseline or Grade 1: suspend dose until toxicity resolves to baseline or Grade 1. Resume at next lower dose.
- Grade 3 or 4: suspend dose until toxicity resolves to baseline or Grade 1. Resume at next lower dose.

Table 7-6: Dose Modification and Management — Nonhematologic Toxicities Excluding Diarrhea, ALT/AST Increased, and ILD/Pneumonitis

CTCAE Grade	Abemaciclib Dose Modifications
Grade 1 or 2	No dose modification is required.
Persistent or recurrent Grade 2 toxicity that does not resolve with maximal supportive measures within 7 days to baseline or Grade 1	Suspend dose until toxicity resolves to baseline or Grade 1. Resume at next lower dose.
Grade 3 or 4	

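### Section 6 and the Section 7.3 tables give inconsistent instructions for treatment-related Grade 3-4 toxicity, and the protocol does not say which prevails

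*Combined protocol and SAP*

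**What the plan says.** Section 6, under the title "General guidelines for dose modifications", sets two rules for treatment-related Grade 3-4 toxicity.

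- Not life-threatening: "dosing should be interrupted and the patients should be followed until the toxicity resolution to grade 1 or lower". Then, if the investigator sees continued clinical benefit: "Following recovery from grade 3 or grade 4 events, study treatment may continue following a dose reduction to the next dose level".
- Life-threatening: "For any grade 3 or grade 4 treatment-related toxicity that is considered by the investigator to be life-threatening, permanently discontinue study treatment".

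Section 7.3 then gives event-specific guidance. For blood counts, Section 7.3.5 says: "The following instructions from Table 7-5 must be used to manage hematologic toxicities". For liver enzymes, Section 7.3.4 says: "The following information in Table 7-3 is to be followed for hepatic monitoring". The VTE table (headed Table 7, at the end of Section 7.3.4) suspends the drug for Grade 3-4 events and adds: "Abemaciclib may be resumed when the patient is clinically stable". Diarrhea (Table 7-1), pneumonitis (Section 7.3.3 and Table 7-2) and other nonhematologic events (Section 7.3.6 and Table 7-6) have their own rows.

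**The concern.** A site managing a severe related toxicity has two places to look, and they do not always agree on whether the patient may restart, how far the event must resolve first, or whether the dose must come down. This is a multisite trial in which the monitoring committee audits conduct against the protocol and reviews deviations (Section 11.1), and a major deviation is a listed ground for withdrawing a patient (Section 4.2). Where the passages cannot both be followed, a site that obeys one breaches the other. The same event could also be handled differently at different sites. That matters most for life-threatening events. It also feeds into the exposure summary (Section 12.3) and the safety tables (Section 12.5.2).

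**Working it through.** No formula applies. The check sets the Section 6 rules against each Section 7.3 table and then looks for any sentence that ranks them. Section 6 covers only treatment-related toxicity, so the comparison is limited to such events. The Grade 3-4 action cells in Tables 7-1 and 7-6 are read as merged with the row above; the text of Section 7.3.6 confirms this for Table 7-6.

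| Event and table | Table's action | Against Section 6, not life-threatening | Against Section 6, life-threatening (permanent stop) |
|---|---|---|---|
| Hematologic, first Grade 3 (7-5) | Hold to Grade 2 or lower; reduction not needed | Recovery grade differs (Section 6: Grade 1 or lower); Section 6 also makes a reduction the condition for continuing | No exception in the table |
| Hematologic, recurrent Grade 3 or Grade 4 (7-5) | Hold to Grade 2 or lower; resume one level down | Recovery grade differs; reduction agrees | Conflict: table directs resumption |
| Diarrhea, Grade 3-4 or hospitalized (7-1) | Hold to Grade 1 or lower; resume one level down | Agrees | Conflict: table directs resumption |
| Other nonhematologic, Grade 3-4 (7-6) | Hold to baseline or Grade 1; resume one level down | Agrees, apart from the baseline alternative | Conflict: table directs resumption |
| VTE, Grade 3-4 (Table 7) | Hold; restart permitted once stable; no recovery grade or reduction given | Differs, but the table only permits restart | Differs; table permits restart with no exception |
| ALT/AST, Grade 4 (7-3) | Discontinue | Differs, but Section 6 only permits continuing | Agrees |
| Pneumonitis, Grade 3-4 (7-2) | Discontinue | Differs, but Section 6 only permits continuing | Agrees |

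**Which rows cannot both be followed.** If a Grade 4 hematologic event is judged life-threatening, one passage orders a permanent stop and the other directs resumption at a lower dose. The diarrhea and other nonhematologic rows have the same problem. For an ordinary Grade 3-4 hematologic event that has come down to Grade 2, Table 7-5 ends the hold while Section 6 continues it. In the last three rows of the table one side is permissive, so a stricter reading can satisfy both.

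**Is precedence stated?** Section 6's one pointer into Section 7.3 concerns the size of dose steps. Section 7.1.1 describes the guidance that follows as recommendations, while Section 7.3.5 makes Table 7-5 compulsory. Neither Section 7.3.5 nor Section 7.3.4 mentions Section 6. Section 6 does write exceptions where they are wanted: pneumonitis is carved out of its Grade 1 and Grade 2 bullets ("For intolerable grade 2 treatment-related toxicities, with the exception of pneumonitis"), but the Grade 3-4 bullet has no carve-out. Life-threatening is defined in Section 7.4 as immediate risk of death from the event, yet the term appears in none of the Section 7.3 tables.

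**The case against.** The strongest reply is that specific guidance displaces general guidance. Section 6 is titled as general, and most of it is worded as what should or may be done. The compulsory wording for Table 7-5 is a strong pointer to that table for ordinary hematologic events. This stands in part: many sites would probably read it that way. But the protocol nowhere says so, and the reading does not settle what happens when an event is life-threatening, where Section 6 is imperative and covers any Grade 3-4 related toxicity.

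A reader might infer that both sets of rules are binding throughout and that every event type receives contrary instructions. The documents do not support that. Only the life-threatening sentence in Section 6 is an imperative. The VTE row permits restart and does not direct it. Stopping at Grade 4 ALT/AST or Grade 3-4 pneumonitis breaches neither passage. Saying that a reduction is not needed does not forbid one. For VTE the overlap may also be small: Section 6 is limited to related events, and the VTE guidance reports no increased rate with single-agent abemaciclib compared with other anticancer agents in similar patients.

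A reader might also infer that the response result is at risk. The primary analysis counts every dosed patient (Section 12.4), and the 28-day calendar runs on through interruptions (Section 9.1), so a hold or reduction does not move the response scan. An early stop or lost exposure could affect an individual patient's outcome, but the documents give nothing from which to estimate how often.

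**Conclusion.** The inconsistency is real and should be corrected. It is sharpest in two places: life-threatening Grade 3-4 toxicity, where Section 6 stops treatment and several tables allow or direct a restart; and hematologic toxicity, where the recovery grade differs and so does the need for a reduction after a first Grade 3. The VTE, Grade 4 ALT/AST and pneumonitis mismatches are secondary.

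The consequence is for patient safety, uniform handling across sites, and the descriptive exposure and safety summaries. Type I error, power and the two-stage design with 9 and then 17 patients do not depend on it. No numerical size can be given, because the documents state no expected frequency for these events. A reader might express it as one patient in 17, but that fraction holds for any single-patient event and says nothing about how many patients would be affected.

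The conclusion assumes that the events are judged treatment-related and that the merged table cells are read as described. It takes no position on which clinical rule is right.

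**What to change.** Reconcile Section 6 with Tables 7-1, 7-2, 7-3, 7-5, 7-6 and the VTE table. Add one statement of precedence between Section 6 and Section 7.3. State explicitly how the Section 6 rule for life-threatening events acts on table rows that allow or direct resumption. The choice of rule in each case belongs to the sponsor and the clinical investigators. The cost is protocol wording and notification of the sites; sample size, endpoints and analysis do not change.

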7. ADVERSE EVENTS AND REPORTING PROCEDURES

7.1 Potential Adverse Events

7.1.1 Follow-up for toxicities

An unscheduled visit should be performed in all cases below where toxicity monitoring is recommended more frequently than defined by the schedule of assessments (Section 9).

Ongoing SAEs at the final safety evaluation visit or the end of study treatment visit (whichever is later) should be followed until they improve becoming non serious events, stabilize, or return to baseline levels. Refer to Section 7 for SAE.

A summary of selected toxicity follow-up recommendations is listed below.

7.2 Abemaciclib dose modification for toxicities

Management of severe or intolerable adverse reactions requires dose reduction, temporary interruption, and/or discontinuation of abemaciclib therapy.

7.3 Guidelines for on-study patient management

7.3.1 Guidelines for Diarrhea Management

Clinical trial data indicates the majority of patients who receive abemaciclib will develop diarrhea. Our experience indicates early identification and intervention for the management of diarrhea has been helpful to patients.

At enrollment, patients should receive instructions on the prompt management of diarrhea. In the event of diarrhea, supportive care measures should be initiated as early as possible. These include the following:

- At the first sign of loose stools, the patient should initiate antidiarrheal therapy (e.g. loperamide) and notify the investigator for further instructions and appropriate follow-up.
- Patients should also be encouraged to drink fluids (e.g., 8 to 10 glasses of clear liquids per day).
- Site personnel should assess response within 24 hours.
- Refer to Table 7-1 for additional information for diarrhea management and dose modification.

Table 7-1: Dose Modification and Management- Diarrhea

At the first sign of loose stools, start treatment with antidiarrheal agents, such as loperamide.

CTCAE Grade	Abemaciclib Dose Modifications
Grade 1	No dose modification is required.
Grade 2	If toxicity does not resolve within 24 hours to \leq Grade 1, suspend dose until resolution. Dose reduction is not required.
Grade 2 that persists or recurs after resuming the same dose despite maximal supportive measures	Suspend dose until toxicity resolves to \leq Grade 1. Resume at next lower dose.
Grade 3 or 4 or requires hospitalization	

Dose level reductions should be made in 50 mg increments. For example, if the starting dose of abemaciclib is 200 mg twice daily, dose reduction 1 would be 150 mg twice daily, dose reduction 2 would be 100 mg twice daily.

7.3.2 General Guidance for Increases in Serum Creatinine and Assessment of Renal Insufficiency

Abemaciclib has been shown to increase serum creatinine due to inhibition of renal tubular transporters without affecting glomerular function (as measured by iohexol clearance). In clinical studies, increases in serum creatinine occurred within the first month of abemaciclib dosing, remained elevated but stable through the treatment period, were reversible upon treatment discontinuation, and were not accompanied by changes in markers of renal function, such as blood urea nitrogen (BUN), cystatin C, or calculated glomerular filtration rate based on cystatin C.

7.3.3 General Guidance for Interstitial lung disease (ILD)/Pneumonitis events

Interstitial lung disease (ILD) /pneumonitis has been identified as an adverse drug reaction for abemaciclib. The majority of events observed in clinical trials were Grade 1 or Grade 2 with serious cases and fatal events reported. Additional information is available in the IB. Monitor for clinical symptoms or radiological changes indicative of ILD/pneumonitis and ask your patients to report any new or worsening pulmonary symptoms such as dyspnea, cough, and fever, and investigate and treat as per your local clinical practice (including corticosteroids as appropriate). If ILD/pneumonitis is suspected, investigations may include imaging, such as high resolution computed tomography, bronchoalveolar lavage, and biopsy as clinically indicated. Discontinue abemaciclib in cases of severe (Grade 3 or 4) ILD/pneumonitis (see also Table 7-2: *refer to dose adjustment table for interstitial lung*

disease/pneumonitis).

Table 7-2: Dose Modification and Management — Interstitial Lung Disease/Pneumonitis

CTCAE Grade	Abemaciclib Dose Modifications
Grade 1 or 2	No dose modification is required.
Persistent or recurrent Grade 2 toxicity that does not resolve with maximal supportive measures within 7 days to baseline or Grade 1	Suspend dose until toxicity resolves to baseline or Grade 1. Resume at next lower dose.
Grade 3 or 4	Discontinue abemaciclib.

7.3.4 General Guidance for Hepatic Monitoring

Alanine aminotransferase (ALT) and aspartate aminotransferase (AST) elevation are considered as ADR with the use of abemaciclib. **The following information in Table 7-3 is to be followed for hepatic monitoring:**

Table 7-3: Dose Modification and Management — Increased ALT/AST

Monitor ALT/AST prior to the start of abemaciclib therapy, every 2 weeks for the first 2 months, monthly for the next 2 months, and as clinically indicated.	
CTCAE Grade	Abemaciclib Dose Modifications
Grade 1 ($>\text{ULN}-3.0 \times \text{ULN}$) Grade 2 ($>3.0-5.0 \times \text{ULN}$)	No dose modification is required.
Persistent or Recurrent Grade 2, or Grade 3 ($>5.0-20.0 \times \text{ULN}$) that does not resolve with maximal supportive measures within 7 days to baseline or Grade 1	Suspend dose until toxicity resolves to baseline or Grade 1. Resume at next lower dose.
$\geq\text{Grade 2} (>3.0 \times \text{ULN})$ with total bilirubin $>2 \times \text{ULN}$, in the absence of cholestasis	Discontinue abemaciclib.
Grade 4 ($>20.0 \times \text{ULN}$)	Discontinue abemaciclib.

To ensure patient safety the investigator should collect specific recommended clinical information and follow-up laboratory tests as shown below in Table 7-4.

Details for hepatic monitoring depend upon the severity and persistence of observed laboratory test abnormalities. If a study patient experiences elevated ALT/AST 5×ULN and elevated TBL 2×ULN, or ALT/AST 8×ULN, liver tests, including ALT, AST, TBL, direct bilirubin, gamma-glutamyl transferase (GGT), and creatine phosphokinase (CPK), should be repeated within 3 to 5 days to confirm the abnormality and to determine if it is increasing or decreasing. If the abnormality persists or worsens, clinical and laboratory monitoring should be initiated by the investigator, based on the hepatic monitoring tests below.

Table 7-4: Hepatic Monitoring Tests for a Hepatic Treatment Emergent Abnormality.

Hematology	Clinical Chemistry
Hemoglobin	Total bilirubin
Hematocrit	Direct bilirubin
Erythrocytes (RBCs - red blood cells)	Alkaline phosphatase (ALP)
Leukocytes (WBCs - white blood cells)	Alanine aminotransferase (ALT)
Differential:	Aspartate aminotransferase (AST)
Neutrophils, segmented	Gamma-glutamyl transferase (GGT)
Lymphocytes	Creatine kinase (CK)
Monocytes	
Basophils	
Eosinophils	
Platelets	
Cell morphology (RBC and WBC)	
Coagulation	Other Chemistry
Prothrombin time, INR (PT-INR)	Acetaminophen
Serology	Acetaminophen protein adducts
Hepatitis A virus (HAV) testing:	Alkaline phosphatase isoenzymes
HAV total antibody	Ceruloplasmin
	Copper
	Ethyl alcohol (EtOH)
	Haptoglobin
	Immunoglobulin IgA (quantitative)
	Immunoglobulin IgG (quantitative)
	Immunoglobulin IgM (quantitative)

HAV IgM antibody	Phosphatidylethanol (PEth)
Hepatitis B virus (HBV) testing:	Urine Chemistry
Hepatitis B surface antigen (HBsAg)	Drug screen
Hepatitis B surface antibody (anti-HBs)	Ethyl glucuronide (EtG)
Hepatitis B core total antibody (anti-HBc)	Other Serology
Hepatitis B core IgM antibody	Anti-nuclear antibody (ANA)
Hepatitis B core IgG antibody	Anti-smooth muscle antibody (ASMA) ^a
HBV DNA ^c	Anti-actin antibody ^b
Hepatitis C virus (HCV) testing:	Epstein-Barr virus (EBV) testing:
HCV antibody	EBV antibody
HCV RNA ^c	EBV DNA ^c
Hepatitis D virus (HDV) testing:	Cytomegalovirus (CMV) testing:
HDV antibody	CMV antibody
Hepatitis E virus (HEV) testing:	CMV DNA ^c
HEV IgG antibody	Herpes simplex virus (HSV) testing:
HEV IgM antibody	HSV (Type 1 and 2) antibody
HEV RNA ^c	HSV (Type 1 and 2) DNA ^c
Microbiology	Liver kidney microsomal type 1 (LKM-1) antibody
Culture:	
Blood	
Urine	

^a Not required if anti-actin antibody is tested.

^b Not required if anti-smooth muscle antibody (ASMA) is tested.

^c Reflex/confirmation dependent on regulatory requirements, testing availability, or both.

General Guidance for Venous Thromboembolic Events

VTE has been identified as an ADR for abemaciclib in combination with endocrine therapy. However, in studies with single-agent abemaciclib use in the metastatic breast cancer or other tumor types, including NSCLC, no increased rates of VTEs were observed as compared to the incidence of VTEs for these particular patient populations who were treated with other

anticancer agents. At this time, the mechanism underlying the association between abemaciclib and the occurrence of VTEs is not known. Venous thromboembolic events have been reported with other CDK4 and 6 inhibitors, and ET is known to be associated with the occurrence of VTEs. Monitor patients for signs and symptoms of deep vein thrombosis and pulmonary embolism and treat as medically appropriate.

Table 7: Dose Modification and Management — Venous Thromboembolic Events

CTCAE Grade	Abemaciclib Dose Modifications
Grade 1 or 2	No dose modification is required.
Grade 3 or 4	Suspend dose and treat as clinically indicated. Abemaciclib may be resumed when the patient is clinically stable.

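### Table 7-3 and Section 6 give different dosing instructions for Grade 3 and Grade 4 ALT/AST elevation, and no sentence says which governs

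*Combined protocol and SAP*

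**What the plan says.** Two places tell the investigator what to do with the dose when ALT/AST rises.

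**Section 6**, under the heading "General guidelines for dose modifications", covers all treatment-related toxicity: "For grade 3 or grade 4 treatment-related toxicity, that is not considered by the investigator to be life-threatening, dosing should be interrupted", and the patient is followed until recovery to Grade 1 or lower. Then: "Following recovery from grade 3 or grade 4 events, study treatment may continue following a dose reduction to the next dose level", on condition that the investigator judges the patient still to be benefiting. For Grade 3 or 4 toxicity "that is considered by the investigator to be life-threatening, permanently discontinue study treatment". Pneumonitis is the only exception named, and only in the Grade 1 and 2 bullets. ALT/AST is not excepted.

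**Section 7.3.4** introduces its table with "The following information in Table 7-3 is to be followed for hepatic monitoring". Table 7-3 requires no change at Grade 1 or 2. Its hold row covers "Persistent or Recurrent Grade 2, or Grade 3" (>5.0–20.0×ULN) "that does not resolve with maximal supportive measures within 7 days to baseline or Grade 1"; the action is to suspend, then resume one level lower. It discontinues at Grade 4 (>20.0×ULN), and at Grade 2 or higher with total bilirubin above 2×ULN without cholestasis.

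**Section 7.2** says that severe or intolerable reactions need a dose reduction, an interruption or discontinuation. It gives no timing.

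**The concern.** In Table 7-3 the 7-day clause directly follows Grade 3, and the no-modification row stops at Grade 2. A first Grade 3 value without the bilirubin rise therefore falls in no row until day 7, and in no row at all if it resolves by then. Section 6 interrupts that patient straight away. At Grade 4 the difference runs the other way: the table ends treatment, while Section 6 leaves a restart open.

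Section 7.3.4 itself lists ALT/AST elevation as an adverse reaction to abemaciclib, and the protocol provides for participating sub-sites. Two sites could treat the same laboratory result differently, each able to point to a protocol instruction.

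**Working it through.** No arithmetic underlies the point; it is a comparison of the rules. All cases below are treatment-related and, except for the last, not judged life-threatening.

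| ALT/AST event | Table 7-3, read literally | Section 6 | Agree? |
|---|---|---|---|
| First isolated Grade 3, before day 7 | No action stated | Interrupt | No |
| Grade 3 resolved within 7 days | No action stated | Interrupted; restart, if any, one level lower | No |
| Grade 3 unresolved at day 7 | Suspend; resume one level lower | Interrupt; may restart one level lower | Yes on hold and dose level from day 7 |
| Grade 4 | Discontinue | Interrupt; may restart one level lower | No |
| Grade 4 judged life-threatening | Discontinue | Discontinue permanently | Yes |

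**Size at Grade 3.** The hold starts on day 0 under Section 6 and as late as day 7 under the literal table, so the range across readings is 0 to 7 days. With the 50 mg steps in Section 7.3.1, a patient on 200 mg twice daily who restarts under Section 6 does so at 150 mg, a reduction of (200 − 150)/200 = 25%. If the value resolves within 7 days, the literal table states no reduction.

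**Size at Grade 4.** From the starting dose, the table gives a permanent stop and Section 6 a possible restart at 150 mg twice daily.

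**Does other text fill the Grade 3 gap?**

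- Section 7.3.6 and Table 7-6 suspend at Grade 3 or 4, but their titles exclude ALT/AST increases.
- The bilirubin row of Table 7-3 acts at once, but only when bilirubin is raised as well.
- The text below Table 7-3 asks for repeat liver tests within 3 to 5 days at ALT/AST 8×ULN, or at 5×ULN with bilirubin 2×ULN. This is monitoring, not a dose action.

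**Was the clause meant for Grade 3?** Table 7-2 uses nearly the same words for Grade 2 alone, "Persistent or recurrent Grade 2 toxicity that does not resolve with maximal supportive measures within 7 days to baseline or Grade 1", and gives Grade 3 or 4 its own row. Table 7-6 is built the same way. If Table 7-3 was meant to follow that pattern, its Grade 3 action would be an immediate hold and a lower dose, in line with Section 6. These are parallels of wording only; neither table applies to ALT/AST.

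**Which text governs?** Section 6 calls itself general, and Section 7.3.4 directs that its table be followed, so the table is the more natural authority. No sentence says so. Section 6 refers to Section 7.3.1 only for the size of the dose steps.

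**The case against.** The strongest reply is that the texts can be read together. Where Table 7-3 is silent, Section 6 supplies the interruption. Section 7.2 requires some dose action for severe reactions, and Sections 7.3.3 and 7.3.5 use that word for Grade 3 and 4. At Grade 4, a permission in general guidelines should not displace a specific order to stop, and stopping complies with both texts. Much of this stands. A careful investigator would probably interrupt at Grade 3 and discontinue at Grade 4. But Section 7.2 gives no timing, and the table's own wording makes an unresolved value at day 7 the trigger at Grade 3. Taking the table as governing settles Grade 4 and leaves the Grade 3 wording as it is.

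A reader might infer more than the documents support:

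- *That Table 7-3 orders full-dose treatment to continue for 7 days.* It does not. It is silent, and an investigator who interrupts breaks nothing in it. Seven further days is an upper bound that ignores Section 6.
- *That Table 7-3 is the only table with this structure.* Table 7-1 also waits, for 24 hours, before suspending at Grade 2 diarrhea.
- *That Section 6 always brings the patient back at a lower dose.* Restarting is optional and depends on continued clinical benefit.
- *That the efficacy result is at risk.* Nothing here touches the two-stage design, the response endpoint or the error rates.

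**Conclusion.** The inconsistency is real and confined to treatment-related ALT/AST elevation not judged life-threatening. At a first isolated Grade 3 value, the start of the hold differs by 0 to 7 days between readings, and a dose reduction on restart may or may not follow. At Grade 4, the difference is between a permanent stop and a permitted restart at a lower dose.

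The Grade 3 part rests on the literal reading of the hold row; it disappears if the 7-day clause was meant for Grade 2 only. The Grade 4 part disappears if the table is taken to govern, which the wording implies but does not state. The number of patients affected cannot be estimated from the documents. This is a safety clarification that should be made; it is not a flaw in the trial's statistical design.

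**What to change.** Make both edits. A precedence sentence alone would leave the Grade 3 wording unresolved.

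1. **Table 7-3.** Split the hold row in two: persistent or recurrent Grade 2 (>3.0–5.0×ULN) "that does not resolve with maximal supportive measures within 7 days to baseline or Grade 1"; and Grade 3 (>5.0–20.0×ULN), with no waiting clause. Keep the present action for both: suspend, then resume one level lower.
2. **Section 6, Grade 3 or 4 bullet.** Add, in substance: *Where a table in Section 7.3 covers the Grade 3 or 4 event, that table takes precedence, except that toxicity the investigator considers life-threatening still requires permanent discontinuation, and treatment may resume only if the investigator judges that the patient is still benefiting clinically.*

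Both exceptions in the second edit are needed. Table 7-5 and the venous thromboembolism table provide for resumption after Grade 4 without mentioning life-threatening events. Table 7-3 does not carry Section 6's clinical-benefit condition. An unqualified precedence sentence would remove both safeguards. No new retest rule is needed, because Section 7.3.4 already has its 3-to-5-day repeat.

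The cost is two short text changes. Some patients with a transient Grade 3 value will be held, and will restart at a lower dose, where the literal table would have required nothing. Section 6 already provides for that.
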